7.2. Analysis Populations

7.2.1. Enrolled Population

The Enrolled Population is defined as all screened patients excluding screen failures.

7.2.2. Intent-to-Treat (ITT) Population/Safety Population

The ITT Population/Safety Population will include all patients who have received at least 1 dose of APX001.

7.2.3. Modified Intent-to-Treat (MITT) Population

The MITT Population will include all patients who satisfy the following criteria:

- Receive at least 1 dose of study drug; and
- Have a confirmed diagnosis of candidemia (blood culture positive for *Candida* spp.) within 96 hours of the start of treatment with APX001

The MITT Population will be the primary population used for the efficacy analysis.

7.2.4. **Per-Protocol (PP) Population**

The Per-Protocol Population will include all patients who satisfy the following criteria:

- Received at least 1 dose of study drug;
- Have a confirmed diagnosis of candidemia within 96 hours of the start of treatment with APX001;
- Did not exceed prior antifungal treatment (per eligibility assessed by the DRC);
- Meet the protocol's key inclusion and exclusion criteria; and
- Have no major protocol violations.

Based on the above criteria, the validity listings will be provided to identify which patients to be excluded from the PP Population. After the study team's review, the decision to exclude a patient from the PP Population will be finalized and a list of patients with major protocol deviations leading to exclusion from the PP Population will be finalized and documented.

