5.6.2 Prohibited Medications and/or Procedures

Eligible patients are prohibited from receiving >2 days (>48 hours) equivalent of antifungal treatment in the 96 hours prior to starting study treatment. The exception to this rule applies only to patients whose candidemia is caused by *Candida* spp. with laboratory-confirmed resistance to the specific antifungal administered, for whom ≤5 days (≤120 hours) equivalent of prior antifungal treatment is permitted. Once on study, patients may not receive concomitant systemic antifungal therapy for the treatment of candidemia while they are receiving APX001.

Patients cannot have received any investigational drug within 30 days prior to dosing.

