3. SAMPLE SIZE DETERMINATION

A sample size of approximately 20 patients will be recruited in this open-label study. No formal statistical assessment for sample size determination has been performed. This sample size is considered adequate to provide the necessary data to evaluate the efficacy and safety of APX001.

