6.4. Definitions for Efficacy Assessments

6.4.1. At End of Study Drug Treatment (EOST)

Treatment Success is defined as meeting all of the following criteria:

- Two consecutive blood cultures negative for *Candida* spp.;
- Alive at EOST; and
- No concomitant use of any other systemic antifungal therapies through EOST.

Treatment Failure is defined as any case that does not meet the criteria for Treatment Success.

Mycological Outcome:

• Eradication is defined as a negative blood culture(s) for *Candida* spp. in the absence of concomitant antifungal therapy through EOST.

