7.4. Efficacy Analysis

7.4.1. Primary Efficacy Analysis

The primary efficacy endpoint is Treatment Success at EOST as determined by the DRC.

The number and percentage of patients with Treatment Success or Treatment Failure at EOST determined by the DRC will be summarized descriptively in total for the MITT Population. The 95% two-sided exact binomial confidence interval will also be presented.

Additional analyses of the primary efficacy endpoint will be performed for the PP Population in the same manner.

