7.4.2.5. DRC Assessments

Reasons for treatment failure according to DRC classifications (i.e. blood cultures did not become negative, or additional antifungals given, or died, or withdrew from study but did not die) will be summarized descriptively at EOST and EOT visits for the MITT and PP populations.

Reasons for relapse or other reasons for not having an outcome of sustained success at follow-up according to DRC classifications, will be summarized descriptively at 2 and 4 weeks after EOT for the MITT and PP populations.

Reasons for death according to DRC classifications (i.e. candidemia probably contributory, candidemia probably not contributory, or not known) will be tabulated for the MITT and PP populations.

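### SAP 7.2.4 can exclude patients from the Per-Protocol set for a violation that is itself a Treatment Failure criterion

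*SAP*

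**What the plan says.** **The prohibition.** Protocol 5.6.2: "Once on study, patients may not receive concomitant systemic antifungal therapy for the treatment of candidemia while they are receiving APX001".

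**The endpoint.** SAP 6.4.1 sets three criteria for Treatment Success at EOST. One is "No concomitant use of any other systemic antifungal therapies through EOST". The section adds: "Treatment Failure is defined as any case that does not meet the criteria for Treatment Success".

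**The PP rule.** SAP 7.2.4 lists five conditions, the last being "Have no major protocol violations". It makes no exception for violations that are also outcomes. Exclusions are settled after review by the study team, in an open-label trial, and the SAP does not say that this review is blind to outcome. Protocol 9.1 leaves the definition of a major violation to the Protocol Deviation Plan, which is not among the documents.

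**The PP outputs.** SAP 7.4.1 repeats the primary analysis in PP. SAP 7.4.2.5 tabulates the Data Review Committee's failure reasons at EOST and EOT for both MITT and PP, and those reasons are "blood cultures did not become negative, or additional antifungals given, or died, or withdrew from study but did not die".

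**The concern.** The same act, adding a systemic antifungal for candidemia on top of ongoing APX001, is both a breach of Protocol 5.6.2 and a failure under SAP 6.4.1. If the breach is graded major, SAP 7.2.4 takes the patient out of PP. The patient is then a failure in the MITT numerator and denominator but absent from the PP calculation. To that extent the PP success rate is conditional on not having failed by this route.

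This matters because PP is the only alternative population planned for the primary endpoint as determined by the committee. A PP rate close to or above the MITT rate would normally be read as support. It would be weaker support if some failures had been excluded because of the event that made them failures. The failure-reason table has the same weakness: a small or empty PP row for added antifungals could be misread as showing that few such failures occurred.

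Reviewing exclusions blind to outcome would not remove the problem, because the ground for exclusion is itself a component of the outcome.

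**Working it through.** **Step 1: is every such breach a failure?** Protocol 5.6.2 covers systemic antifungals given for candidemia while the patient is receiving APX001. SAP 6.4.1 covers any other systemic antifungal through EOST, which falls after APX001 dosing ends. The first set lies inside the second, so anyone removed for this breach is a failure by definition. The reverse does not hold. An antifungal for another indication, or one started after APX001 has stopped, may be a failure without breaching 5.6.2.

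**Step 2: does another rule keep these patients in PP?** SAP 7.1.2 keeps dropouts and patients with missing outcomes in the efficacy denominator, but it does not address who belongs to PP. SAP 7.4.2.5 implies that some patients with added antifungals are in PP, but it does not amend SAP 7.2.4. Nothing supplied settles the matter.

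**Step 3: size.** The plan has no figure to reproduce. SAP 3 states "A sample size of approximately 20 patients will be recruited in this open-label study" and "No formal statistical assessment for sample size determination has been performed", and no expected success rate is given.

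Inputs:
- n = 20 (SAP 3)
- x = 12, 14 or 16 successes (assumption)
- k = 1 to 3 failures removed for this breach (assumption)
- no other PP exclusions (assumption)
- two-sided 95% exact binomial (Clopper-Pearson) intervals, as planned in SAP 7.4.1: "The 95% two-sided exact binomial confidence interval will also be presented"

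Formulas: MITT success = x/n; PP success = x/(n − k); shift = x/(n − k) − x/n = xk/[n(n − k)].

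Example: x = 14, k = 2 gives 14/18 − 14/20 = 77.8% − 70.0% = 7.8 points.

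| x | MITT, k = 0 | PP, k = 1 | PP, k = 2 | PP, k = 3 |
|---|---|---|---|---|
| 12 | 60.0% (36.1–80.9) | 63.2% (38.4–83.7) | 66.7% (41.0–86.7) | 70.6% (44.0–89.7) |
| 14 | 70.0% (45.7–88.1) | 73.7% (48.8–90.9) | 77.8% (52.4–93.6) | 82.4% (56.6–96.2) |
| 16 | 80.0% (56.3–94.3) | 84.2% (60.4–96.6) | 88.9% (65.3–98.6) | 94.1% (71.3–99.9) |

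Shift from MITT:
- one removal: +3.2 to +4.2 points
- two removals: +6.7 to +8.9 points
- three removals: +10.6 to +14.1 points

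The step from each removal to the next runs from 12/19 − 12/20 = 3.2 points to 16/17 − 16/18 = 5.2 points. If the same patients stay in PP as failures, and nothing else differs, the PP rate equals the MITT rate.

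**The case against.** The strongest reply is that removal is only a possibility. The Protocol Deviation Plan may not grade this event as major, and the study team may not exclude the patient. That stands: a reader might infer that PP will drop these failures, but the documents show only that it can.

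The route is also narrow. Protocol 8.5.2 allows study treatment to be stopped for lack of response. A patient who stops APX001 and then starts another antifungal has not breached 5.6.2. Protocol 4.4 lists the need for a prohibited medication among the withdrawal reasons, and withdrawal is a separate failure reason in SAP 7.4.2.5. It would therefore be wrong to say that non-responders in general leave the denominator.

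Three further inferences are tempting and not supported:

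- **SAP 7.2.4 and 7.4.2.5 flatly contradict each other.** They do not. The added-antifungal row can be filled by patients whose antifungal use lies outside 5.6.2. The two sections fit poorly, because the row would omit the on-treatment cases, but both can be carried out.
- **PP must look better than MITT.** PP also excludes patients for eligibility, prior antifungal treatment and other violations, and some of those may be successes. Only the effect of this one route has a known direction.
- **PP is the only check on the primary result.** SAP 7.4.2.1 plans Investigator-assessed outcome at EOST, and SAP 7.4.2.2 plans eradication at EOST, each in MITT as well as PP.

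It is also fair to say that the analyses are descriptive, that no decision rule uses PP, and that exclusions for major deviations will be documented and failure reasons tabulated in MITT. A careful reader could trace an exclusion. That limits the harm but does not correct the PP estimate.

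**Conclusion.** The point holds in conditional form. SAP 7.2.4 has no exception for violations that are themselves Treatment Failure criteria, and an antifungal for candidemia added during APX001 is both. If the Protocol Deviation Plan grades it major, this exclusion route can remove only failures from PP, and its own effect on PP success is upward.

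With about 20 patients, single classification decisions are visible: about 3 to 5 points for each of the first three removals, and about 11 to 14 points for three together. These sizes rest on assumed success counts of 12 to 16 out of 20, assumed numbers of removals, and no other PP exclusions. How often the event will occur is unknown.

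The damage is confined to the PP analyses. The primary MITT result does not change. This is worth correcting because it is cheap and precise, but it does not threaten the main conclusion.

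**What to change.** Before database lock, add to SAP 7.2.4:

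> *Post-dose systemic antifungal use that is itself a Treatment Failure criterion is not grounds for exclusion from the PP Population; the patient stays in PP and is counted as a Treatment Failure.*

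Align the grading in the Protocol Deviation Plan with this sentence, and state in SAP 7.4.2.5 that the PP failure-reason table includes these patients.

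The exception should go no wider. Stopping study drug, for toxicity or any other reason, is not one of the SAP 6.4.1 criteria and should not be listed as a failure component. A patient with a separate major violation would still be excluded on that ground.

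The cost is one sentence and a consistency check, with no change to treatment or data collection. The downside is a PP rate that may be slightly less favourable. If the Protocol Deviation Plan already handles the event this way, the sentence only records it.

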7.3. Patient Data and Study Conduct

7.3.1. Patient Disposition

Patient disposition will be summarized for the Enrolled Population and ITT Populations in total. The following patient disposition categories will be included in the summary:

- Patients who received study drug;
- Patients who did not receive study drug;

- Patients who completed 14 days of study drug;
- Patients who did not complete 14 days of study drug (and reason);
- Patients who took protocol-allowed step-down further antifungal treatment;
- Patients who did not take protocol-allowed step-down further antifungal treatment;
- Patients who completed the study; and
- Patients who did not complete the study (and reason).

For patients who did not complete 14 days of study drug and patients who did not complete study, a summary will be provided by reason of discontinuation. In addition, the total number of patients for each defined population will be tabulated.

7.3.2. **Protocol Deviations**

The number of patients with at least one reportable protocol deviation, and the number of patients with at least one reportable deviation in each category defined in the study protocol deviation plan will be presented in total based on the Enrolled Population and ITT Population.

Protocol deviations will also be listed by patient.

7.3.3. Demographic and Baseline Characteristics

The following demographic and baseline characteristics will be summarized:

- Age (years) and age categories (<65 years, \geq 65 years);
- Sex;
- Race;
- Ethnicity;
- Height (cm);
- Weight (kg);
- Body mass index (BMI) (kg/m2);
- APACHE II score and categories (<10, 10-19, 20-30, or >30); and
- ICU vs. non-ICU.

Demographic and Baseline characteristics will be summarized with descriptive statistics or counts and percentages of patients as appropriate in total for the Enrolled Population, ITT, MITT, and PP Populations.

7.3.4. Baseline Infection Characteristics

All baseline pathogens will be summarized with counts and percentages of patients in total for the MITT and PP Populations.

Details of organism identification and antifungal susceptibility results including MICs of all antimicrobials tested will be listed by patient. Both data from local and central microbiological laboratories will be listed.

7.3.5. Medical History

The primary underlying condition leading to candidemia and other medical history will be coded to system organ class (SOC) and preferred term (PT) using the Medical Dictionary for Regulatory Activities (MedDRA, Version 20.1).

Counts and percentages of patients with primary underlying condition and other medical history by SOC and PT will be summarized in total based on the ITT and MITT Populations.

All medical history will be listed by patient.

7.3.6. Prior and Concomitant Medications

Prior and concomitant medications will be coded to anatomical therapeutic chemical (ATC) class and preferred term using the World Health Organization (WHO) Drug Dictionary (September 2017 B3 Version).

Prior medications are medications used before the first dose of study drug. Concomitant medications are medications that were taken on or after first dose of study drug.

The number and percentages of patients who receive the following prior and concomitant medications will be summarized by ATC class and preferred term in total for the ITT and MITT Populations:

- Prior medications;
- Concomitant medications;
- Prior antifungals;
- Protocol-allowed step-down fluconazole or alternative concomitant antifungals; and
- Additional concomitant antifungals except for protocol-allowed step-down antifungals.

All prior and concomitant medications and procedures will be listed by patient.

7.3.6. **Dosing and Extent of Exposure**

7.3.6.1. Study Drug

Days of exposure to study drug will be summarized for intravenous and oral dose in overall. Days of exposure to study drug will be calculated as the last dose date of study drug – first dose date of study drug + 1. Overall days of exposure to study drug will be summarized in total based on the ITT, MITT, and PP Populations with descriptive statistics and with counts and percentages of patients with exposure in the following categories:

- $\leq 7 \text{ days};$
- >7 to \leq 14 days; and

• >14 days

For patients who switch from intravenous to oral dose, the compliance rate for oral dose will be calculated as the total amount of doses received divided by the total amount of doses expected then multiplied by 100. The total amount of expected doses is the number of medication days multiplied by the expected doses per day. Number of medication days is the total number of days from the date of the first oral dose of study drug to the date of the last oral dose of study drug.

Percent compliance with oral study drug will be calculated using the following formula:

%compliance =
$$\frac{\text{total amount of doses received * 100}}{\text{expected doses per day * total number of medication days}}$$

The compliance rate for oral dose will be summarized with descriptive statistics in total for the ITT, MITT, and PP Populations. In addition, contingency tables will be provided to show the number and percentage of patients in each treatment group with compliance in the following categories: <80% and $\ge80\%$.

7.3.6.2. Overall Antifungal Treatment

After completion of 14 days study drug therapy, if further antifungal treatment is indicated to complete treatment of candidemia in accordance with standard practice guidelines, fluconazole (unless susceptibility results warrant alternative antifungal therapy) may commence for up to a further 7 days.

The overall duration of antifungal treatment (study drug + protocol-allowed step-down further antifungal treatment) is defined as the last dose date of step-down further antifungal treatment – first dose date of study drug + 1. If patient did not take any step-down further antifungal treatment, the duration of antifungal treatment will be the same as duration of study drug.

The overall duration of antifungal treatment will be summarized in total based on the ITT, MITT, and PP Populations with descriptive statistics and with counts and percentages of patients with exposure in the following categories:

- $\leq 14 \text{ days};$
- >14 to \leq 21 days; and
- >21 days

The number and percentage of patients who took protocol-allowed step-down further antifungal treatment will also be tabulated based on the ITT, MITT, and PP Populations.

7.4. Efficacy Analysis

7.4.1. Primary Efficacy Analysis

The primary efficacy endpoint is Treatment Success at EOST as determined by the DRC.

The number and percentage of patients with Treatment Success or Treatment Failure at EOST determined by the DRC will be summarized descriptively in total for the MITT Population. The 95% two-sided exact binomial confidence interval will also be presented.

Additional analyses of the primary efficacy endpoint will be performed for the PP Population in the same manner.

7.4.2. Secondary Efficacy Analysis

Descriptive statistics will be provided for secondary efficacy endpoints as the following.

7.4.2.1. Treatment Outcome

Number and percentage of patients in the MITT and PP Populations with treatment outcomes (Treatment Success and Treatment Failure) at EOT as determined by the DRC will be presented descriptively, along with the 95% two-sided exact binomial confidence interval.

Number and percentage of patients in the MITT and PP Populations with treatment outcomes (Treatment Success Sustained, Clinical Relapse, and Other [Non-Relapse]) at 2 and 4 weeks after EOT as determined by the DRC will be presented descriptively, along with the 95% two-sided exact binomial confidence interval.

Number and percentage of patients in the MITT and PP Populations with treatment outcomes (Treatment Success and Treatment Failure) at EOST and EOT as determined by the Investigator will be tabulated, along with the 95% two-sided exact binomial confidence interval.

7.4.2.2. Mycological Outcome

The number and percentage of patients in the MITT and PP Populations with Eradication at EOST and EOT will be summarized descriptively, along with the 95% two-sided exact binomial confidence interval.

The number and percentage of patients in the MITT and PP Populations with Recurrence at 2 and 4 weeks after EOT as determined by the Investigator will be summarized descriptively, along with the 95% two-sided exact binomial confidence interval.

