6.2. Secondary Efficacy Endpoints

The secondary efficacy parameters include the following:

- Time to first negative blood culture;
- Percentage of patients with Mycological Outcomes at EOST, EOT, and 2 and 4 weeks after EOT;
- Percentage of patients with Treatment Success at EOT, and 2 and 4 weeks after EOT as determined by the DRC;

- Overall survival at Study Day 30; and
- Number of patients with TEAEs.

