6.4.3. At Follow-up (2 Weeks and 4 Weeks After End of Antifungal Treatment)

- Recurrence (mycological) is defined as a mycologically confirmed infection based on blood culture with the same Baseline *Candida* spp. during the 4 weeks after EOT.
- Relapse (DRC Assessment) is defined as re-occurrence of *Candida* in blood culture during the Follow-up Period, or diagnostic parameters indicative of recurrence or late spread of the *Candida* infection.

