7.1.2. Handling of Dropouts and Missing Data

Subjects who dropped out or had missing outcome data will be included in the denominator for efficacy analyses. A clinical failure occurring at an earlier time point will be carried forward to the subsequent visits.

In cases of missing or incomplete dates (e.g. Adverse event [AE] and concomitant medications), the missing component(s) will be assumed as the most conservative value possible. For example, AEs with missing start dates, but with stop dates either overlapping into the treatment period or missing, will be counted as treatment-emergent, taking the worst-case approach. When partial dates are present in the data, both a partial start date and/or a partial stop date will be evaluated to determine whether it can be conclusively established that the AE started prior to the start of study drug or ended prior to the start of study drug. If the above cannot be conclusively established based on the partial and/or present dates, then the AE will be considered as treatment-emergent. Actual data values as they appear in the original eCRF will be presented in the data listings.

Missing values for other variables will not be imputed and only observed values will be used in data analyses and summaries.

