7.4.2.3. Time to First Negative Blood Culture

Time to first negative blood culture is defined as the number of days from first dose date of study drug to the date of first negative blood culture plus 1.

Time to first negative blood culture will be summarized in total using descriptive statistics for the MITT and PP Population.

In addition, the Kaplan-Meier estimate of the median time to first negative blood culture and the associated 95% confidence interval will be presented. Patients without a negative blood culture at post-baseline visits will be censored at the last assessment date.

7.4.2.4. Overall Survival at Study Day 30

Overall survival at Study Day 30 is defined as patient alive by study day 30.

The number of percentage of patients alive or dead by Study Day 30 will be summarized for the MITT and PP Population.

Time to death is defined as the number of days from first dose date of study drug to the date of death from any cause plus 1. Patients without death or lost to follow-up will be censored on the last date the patient is known to be alive. The Kaplan-Meier estimate of the median time to death and the associated 95% confidence interval will be presented.

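### Recurrence is reported only over all MITT/PP patients without requiring earlier clearance, so it is not a risk of recurrence after clearance; the Day 30 survival percentage has no confidence interval

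*SAP*

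**What the plan says.** **Recurrence.** SAP 6.2 lists as a secondary endpoint "Percentage of patients with Mycological Outcomes at EOST, EOT, and 2 and 4 weeks after EOT". At the two follow-up visits Recurrence is the only mycological outcome defined. Under SAP 6.4.3 (and protocol 7.4.3) it "is defined as a mycologically confirmed infection based on blood culture with the same Baseline" species, in the 4 weeks after EOT. Neither document adds a condition of earlier clearance. SAP 7.4.2.2 plans "The number and percentage of patients in the MITT and PP Populations with Recurrence at 2 and 4 weeks after EOT", as judged by the Investigator, with an exact 95% interval.

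SAP 7.1.2 adds two rules: "Subjects who dropped out or had missing outcome data will be included in the denominator for efficacy analyses" and "A clinical failure occurring at an earlier time point will be carried forward to the subsequent visits". MITT entry (SAP 7.2.3) needs one dose and confirmed candidemia, not clearance.

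The Data Review Committee (DRC) has its own follow-up categories in SAP 7.4.2.1: "Treatment Success Sustained, Clinical Relapse, and Other [Non-Relapse"]. SAP 7.4.2.5 tabulates "Reasons for relapse or other reasons for not having an outcome of sustained success at follow-up according to DRC classifications".

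**Day 30 survival.** This is also a named secondary endpoint. SAP 7.4.2.4 says "The number of percentage of patients alive or dead by Study Day 30 will be summarized for the MITT and PP Population". No interval is attached to that percentage, and SAP 7.1.1 supplies none by default for categorical variables. The section's only interval belongs to the Kaplan-Meier median time to death. Patients who have not died or are lost are censored when last known alive.

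**The concern.** A clinician will read a Recurrence percentage as how often the infection returned once it had cleared. The planned figure differs from that in two ways that pull in opposite directions.

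- Patients who died or had no follow-up culture, without a positive culture after EOT, stay in the denominator and in effect count as non-recurrences. So do never-cleared patients who are not cultured again. Keeping missing patients in the denominator is conservative for Treatment Success; for an adverse outcome it is not.
- A never-cleared patient who is still positive with the baseline species after EOT meets the definition literally. Persistent candidemia would then be counted as recurrence.

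The carry-forward rule speaks of a clinical failure. It does not say how a patient who had not cleared by EOT enters the Recurrence table.

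For survival, a named endpoint in about 20 patients would be reported without a measure of precision, while the planned interval is for a quantity that will probably not be estimable.

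**Working it through.** The plan states no figure to reproduce: SAP 3 gives about 20 patients and no formal calculation, and the documents give no clearance, recurrence or mortality rate. All counts below are assumptions, with MITT N = 20. Intervals for proportions are exact (Clopper-Pearson) 95%, the SAP's own method: lower limit = Beta(0.025; x, n − x + 1), upper limit = Beta(0.975; x + 1, n − x).

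**1. Recurrence.** Assume 15 of 20 patients cleared by EOT, 12 of the 15 have a follow-up culture, and 2 recur.

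| Summary | Count | % (95% CI) |
|---|---|---|
| As planned, all MITT | 2/20 | 10.0 (1.2–31.7) |
| All cleared patients | 2/15 | 13.3 (1.7–40.5) |
| Cleared with a follow-up culture | 2/12 | 16.7 (2.1–48.4) |
| Extreme bound: the 3 uncultured cleared patients all recurred | 5/15 | 33.3 (11.8–61.6) |
| As planned, plus 1 never-cleared patient still positive | 3/20 | 15.0 (3.2–37.9) |
| As planned, plus 2 such patients | 4/20 | 20.0 (5.7–43.7) |

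With no persistent case counted, the planned 10.0% is below both 13.3% and 16.7%. One persistent case moves it above 13.3%; two move it above 16.7%. The direction of the difference is therefore not fixed, and the planned table alone would not show which case applies.

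**2. Precision of Day 30 survival.** The omitted interval is wide: 18/20 alive = 90.0% (68.3–98.8), 16/20 = 80.0% (56.3–94.3), 14/20 = 70.0% (45.7–88.1).

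**3. Whether the median's interval can replace it.** Without early censoring, the Kaplan-Meier curve reaches 0.5 only at the 10th death of 20. With 4 deaths of 20 and no censoring, S = 0.80 and its log-log lower limit is 0.551. That is above 0.5, so with 4 or fewer deaths the lower limit of the median is not estimable either.

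| Assumed mortality | P(10 or more deaths of 20) | P(4 or fewer deaths of 20) |
|---|---|---|
| 20% | 0.3% | 63% |
| 30% | 4.8% | 24% |
| 40% | 24% | 5% |

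**4. A Kaplan-Meier estimate at Day 30.** Assume deaths on Days 5, 9, 14 and 22 and censoring on Days 8 and 16. Then S(30) = (19/20)(17/18)(16/17)(14/15) = 0.788, log-log 95% CI 0.528–0.915. The method the SAP already uses for time to death gives a usable estimate here, while the median is not reached.

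**5. How many patients could have unknown Day 30 status.** The last visit is 4 weeks (+4 days) after EOT. EOT on Day 2 gives Days 30–34 (2 + 28, + 4); EOT on Day 14 gives Days 42–46. Patients who complete follow-up are thus seen on or after about Day 30. For the others, protocol 4.4 requires contact attempts for those lost, and protocol 8.3 requires SAE reporting to 30 days after the last dose. The gap is narrow.

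**The case against.** **The all-patient proportion is legitimate.** It follows the rule set for every efficacy analysis, and the SAP never calls it a risk after clearance. This stands: the figure should be kept, and the point is only that nothing beside it answers the other question. Eradication counts and patient listings would allow a conditional rate later, but its denominator would then be chosen after the data are seen.

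**Durability is already analysed.** The DRC tables report sustained success and relapse with exact intervals, and reasons for failure that include cultures never turning negative, death and withdrawal. This stands in large part, so a reader should not infer that durability is ignored. But Relapse also admits other diagnostic evidence, is judged by a different assessor, and is again a percentage of all MITT/PP patients.

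**Why not require Eradication at EOT?** This repair is tempting, but the documents do not support it. Eradication at EOT (SAP 6.4.2, protocol 7.4.2) also requires no additional antifungal beyond the allowed step-down. A patient who cleared, received another antifungal and then regrew the same species could no longer count, although that is a true recurrence after clearance. It would also change the planned numerator and depart from the protocol definition, while SAP 9 declares no changes.

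**Unknown patients counted as alive.** A reader might infer that with 14 alive, 4 dead and 2 unknown the table could show 16/20 = 80.0% alive. Nothing in the text says so. SAP 7.1.2 keeps them in the denominator, and the natural reading is 14/20 = 70.0%. What remains is that no row for unknown status is named.

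**The study is small and descriptive, and all counts are assumed.** True, and the intervals compared overlap heavily. An exact interval can also be derived from the planned count. That limits the size of the point.

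**Conclusion.** Both parts hold, at modest size. The planned Recurrence percentage is valid for all treated patients with confirmed candidemia, but it cannot be read as a risk of recurrence after clearance. A reader might infer that it understates that risk; the documents do not support a fixed direction, because a still-positive patient who never cleared meets the definition. In the illustration the planned figure runs from 10.0% to 20.0%, against 13.3% among all cleared patients and 16.7% among those cultured.

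Day 30 survival lacks the interval given to the treatment and mycological outcomes. The planned median would be reached with probability of about 24% or less at assumed mortality up to 40%, taking N = 20 and no early censoring.

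The primary endpoint is not affected. This is a cheap improvement, not a flaw that undermines the study.

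**What to change.** **SAP 7.4.2.2.** Leave the protocol definition and the planned MITT/PP Recurrence proportion unchanged. Add a supplementary summary of Recurrence among patients with documented blood-culture clearance by EOT, meaning that the last blood culture at or before EOT is negative, whatever additional antifungals were given. Report it over all such patients and over those with at least one follow-up culture by that visit, each with the exact 95% interval. Show separate rows for still positive or never cleared, died, and no follow-up culture, so that persistent candidemia is separated from recurrence. Record the addition in SAP 9.

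**SAP 7.4.2.4.** Keep the percentage and the median. Add the exact 95% interval for the percentage alive at Day 30, with all MITT patients in the denominator and unknown status not counted as alive but shown in its own row. Add the Kaplan-Meier survival estimate at Day 30 with a log-log 95% interval.

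**Cost.** SAP wording and table shells, using data already planned for collection, with no protocol amendment because the definition stays. The downside is a few more rows, wide intervals, and a supplementary summary that conditions on a post-baseline result, which is why the all-patient proportion stays beside it.
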